### 3.7 Table of endpoints/outcomes

Objectives	Outcome Measures	Timepoint(s) of evaluation of this outcome measure (if applicable)
Primary Objective To compare the effect of vitamin D supplementation on executive function	Trails-B measure, completed in one session online on the PROTECT website.	Baseline, six, 12, and 24 months Primary endpoint is 24 months
Secondary Objectives To compare the effect of vitamin D supplementation on cognition, function and behaviour  To establish the cost-effectiveness of vitamin D supplementation	Cognitive Test Battery (Paired Associate Learning, Digit Span, Self-Ordered Search Task [working / spatial memory tasks], Switching Stroop and Baddeley Grammatical Reasoning [Executive Function Tasks  Instrumental Activities of Daily Living Scale  Mild Behaviour Impairment Scale  EQ5D scale	Baseline, six, 12, and 24 months
Tertiary Objectives Example: To monitor safety and compliance of vitamin D supplementation in the trial cohort  To explore participant experience of taking part in an online trial	Adverse Event and Serious Adverse Event reporting in response to email prompts, or proactively by participants through the website, telephone or email  Anonymous survey	Quarterly  24 months (after study completion)

#### 4 TRIAL DESIGN

A two-year two-arm placebo-controlled double-blinded randomised controlled trial in 584 participants.

#### 5 TRIAL SETTING

The trial will be run remotely, with participants receiving study tablets at home, and completing all assessments online via the PROTECT website.

#### 6 PARTICIPANT ELIGIBILITY CRITERIA

##### 6.1 Inclusion criteria

- Age 50 and over
- Already registered as a participant on the PROTECT study
- Fulfilling research criteria for dementia risk: Either (1) Performing at least one Standard Deviation below age-matched population norms in one cognitive test as measured using the validated PROTECT and COGTRACK™ cognitive test batteries; and/or (2) Reporting subjective memory concerns; and/or (3) Reported family history of dementia
- Fulfilling criteria for vitamin D deficiency risk: Defined by a self-reported scale to be completed on registration.
- Access to a computer and the internet.

## 6.2 Exclusion criteria

- Already taking part in another active interventional clinical trial
- Regularly take any supplement containing vitamin D. If the supplement is prescribed for a pre-existing condition the participant will be excluded. If the supplement is bought over the counter the participant will have the option of stopping the supplement and re-registering for the trial after a 28-day washout period.
- Diagnosis of dementia
- Taking the medication Digoxin (Lanoxin)
- History of physiological condition that specifically necessitates the avoidance of Vitamin D supplementation e.g. risk of renal stones

## 7 TRIAL PROCEDURES

### 7.1 Recruitment

#### 7.1.1 Participant identification

Recruitment of participants will be achieved through the PROTECT study cohort. The study operates entirely online, with existing participants receiving email reminders to log in and complete outcome assessments or register for new trials. All participants have given consent for contact and have full datasets for pre-screening. The PROTECT study has existing ethical approval (Ref: 13/LO/1578) and has been running since April 2015.

Participants with dementia risk will be identified anonymously through pre-screening of the existing PROTECT database. This will involve identification of people fulfilling the criteria for AACD through screening of cognitive test scores, those fulfilling criteria for family history through self-reported data provided on family history of dementia and those with subjective concerns about their cognitive health. Participants in the PROTECT study will be contacted via email and invited to take part in VitaMIND. The email will contain a link to the dedicated trial section of the site. Individuals known to fulfil the AACD and family history criteria will be automatically flagged for eligibility by the online system. Participants will also be asked if they have subjective concerns about their cognitive health in order to capture this third eligibility criterion. In the event that additional recruitment is required new participants will be approached through NHS Trust memory clinics, the Exeter 10,000 cohort of older adults (existing approval and consent for contact), through partner platforms such as Join Dementia Research (an online self-registration service that enables volunteers with memory problems, carers of those with memory problems and healthy volunteers to register their interest in taking part in research), and through national publicity.

10% of the study cohort will be randomly selected for compliance testing via a finger prick blood test. Participants in this sub-group will confirm their willingness to participate in the blood testing during registration and those selected will be sent a blood test kit in their welcome pack.

#### 7.1.2 Screening

IRAS ID: 247136

Protocol version: 8.0

Date: 5th May 2023

A series of screening steps will be completed to confirm eligibility. This will consist of:

- Confirmation of eligibility criteria (defined above) – Where possible these criteria will be screened by filtering of existing PROTECT data prior to participant contact but will be confirmed at registration using a tick-box process. New criteria will be screened at registration by completion of yes/no tick-box questions, covering:
  - Family history of dementia: Participants will be asked whether they have a family history of cognitive impairment or dementia.
  - Subjective concerns about cognitive health: Participants will be asked whether they are currently worried about their memory or other aspects of brain health.
  - Contra-indicated medication: Participants will be asked to state whether they are currently taking Digoxin. If so, they will be excluded.
  - Existing Vitamin D supplementation: As described above, participants taking existing vitamin D supplements will be offered the opportunity to re-register after a 28-day washout period, unless the supplements are prescribed by a medical practitioner.
  - Contraindication for vitamin D supplements: Participants will be asked if they have been advised by a medical practitioner not to take Vitamin D supplements due to an existing medical condition, for example due to risk of kidney stones. If so, they will be excluded.
  - Involvement in an ongoing interventional study
- Dementia Risk: Increased dementia risk will be a pre-requisite for invitation to the study. Participants will be identified as described in section 6.1. The risk profiles included in this protocol are still exploratory, and relevant to research purposes only. Therefore, participants will not be informed if they fulfil this criterion since communications of early cognitive impairment (which are too early for any clinical detection, treatment or support) carry an extremely high risk of unwarranted distress.
- Vitamin D deficiency risk: Participants will complete a screening questionnaire during the registration and consent process. This will involve completion of a tick-box list of the following pre-set risk factors:
  - BMI
  - Age
  - Smoking status
  - Self-rated health
  - Outdoor/physical activity
  - Osteoporosis
  - Marital status
  - Ethnicity
  - Alcohol consumption
  - Month of assessment

Participants fulfilling criteria for vitamin D deficiency will continue into the trial. Any participants not fulfilling criteria will be informed and excluded at this point.

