### 8.4 Supplement storage and supply

Vitamin D tablets and placebo will be manufactured by HealthSpan Ltd and packaged in blister packs of 28 pills, with days of the week marked on the packet. The shelf life of capsules is a conservative two years, but to ensure dosing capsules will be delivered quarterly unless the government COVID-19 alert is level 2 or higher in which case a larger supply will be sent to mitigate against the risk of site closure due to a lockdown. Capsules can be stored at room temperature with no additional special requirements.

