### 8.6 Dosage schedules

Participants will be instructed to take one tablet per day for two years. For the active supplement each dose will contain 4000IU of Vitamin D3.

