### 8.7 Known drug reactions and interaction with other therapies

Possible severe interaction with Digoxin. Participants taking this medication will be excluded from the trial.

*Guidance on taking supplements:* Participants will be instructed to take one tablet per day. There are no known side effects of vitamin D supplementation within the dose used in this study. In the event of an extreme overdose (usually occurring after taking consistent high doses of 60,000IU per day for several months) symptoms include nausea and vomiting, weakness and frequent urination, followed by osteopain and kidney complications. This is extremely unlikely to occur within this trial but participants will be guided to be aware of symptoms in case of an overdose and provided with clear signposting to contact their GP for support if this occurs, in addition to reporting the event to the study administrator.

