### 8.11 Assessment of compliance with treatment

**Compliance Monitoring:** Monitoring of participant use of the tablets will be achieved through a 'medication diary' on the PROTECT site which will ask participants to provide a quarterly tablet count, both of which will be entered online. This will also be supported through reminder emails and regular newsletters from the PROTECT study. This process is anticipated to be highly effective. However, since it is reliant on participant adherence and fidelity, an additional sub-group of compliance testing will also be performed (see below).

**Sub-group Compliance Monitoring:** In addition a sub-group of 10% of the total cohort (n = 58) will be recruited to complete a finger prick test to analyse blood levels of Vitamin D3 metabolites at baseline and primary endpoint (24 months) as a further compliance measure. This process will be delivered through partnership with the Sandwell and West Birmingham NHS foundation Trust test facility. This process will involve:

- Sub-group compliance participants allocated to the first 10% of randomised participants
- Study administrator attaches participant identifier label to test kit and posts kit to participant
- Participants will receive a test kit to complete at home, involving a short finger prick test
- Participants use pre-addressed envelope to send their completed test to the Sandwell and West Birmingham NHS Foundation Trust test laboratory
- Laboratory completes Vitamin D3 analysis according to published protocols using anonymised sample identifiers. No sample is retained after analysis
- Laboratory returns anonymised test results to study team

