## 9.2 Operational definitions for (S)AEs

### *Adverse Event*

An AE is defined as any medical event occurring to a participant during the two-year study that requires medical intervention.

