## 9.3 Recording and reporting of AEs and SAEs

All AEs and SAEs occurring from the time of **start of trial treatment** until the end of the trial will be reported by participants using an online form. Participants will be prompted to enter any details of events at each login event (quarterly) and encouraged to report any event proactively using the online form or by contacting the study team by telephone and email. All AEs will be logged in REDCap Cloud.

Receipt of an AE or SAE on the system will prompt review by the study team. AEs will be reviewed by at least two members of the TMG. SAEs will be reviewed by a study clinician within

24 hours. The participant, and their GP where appropriate, will be contacted for follow-up and recommended action. The Sponsor will also be informed.

AE and SAE actions and monitoring will be recorded electronically, including the following information

- full details in medical terms and case description
- event duration (start and end dates, if applicable)
- action taken
- outcome
- seriousness criteria
- causality (i.e. relatedness to trial drug / investigation), in the opinion of the investigator
- whether the event would be considered anticipated.

Any change of condition or other follow-up information will be faxed to the Sponsor as soon as it is available or at least within 24 hours of the information becoming available. Events will be followed up until the event has resolved or a final outcome has been reached.

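### Digoxin is specifically checked only at registration; during two years of dosing it would surface only indirectly, and no clear rule says capsules then stop (low severity)

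*Protocol*

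**What the plan says.** Digoxin appears in three places in the protocol. Section 6.2 lists current use as an exclusion criterion. Section 7.1.2 turns that into a tick-box question at registration: "Participants will be asked to state whether they are currently taking Digoxin. If so, they will be excluded". Section 8.7 gives the reason: "Possible severe interaction with Digoxin. Participants taking this medication will be excluded from the trial". It is the only drug interaction listed there.

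Exposure runs well beyond registration. Section 8.6 states: "Participants will be instructed to take one tablet per day for two years". Under 8.4, "to ensure dosing capsules will be delivered quarterly", apart from larger shipments at raised COVID-19 alert levels.

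The main safety route during dosing is adverse event reporting. Section 9.2 sets the threshold: "An AE is defined as any medical event occurring to a participant during the two-year study that requires medical intervention". Section 9.3 prompts participants for events at each quarterly login and encourages reports at any time by form, telephone or email. At least two Trial Management Group members review adverse events, and a study clinician reviews serious ones within 24 hours. The participant, and the GP where appropriate, is then contacted. Section 9.4 adds initial review by the investigator, trial coordinator and a clinical delegate.

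Section 7.8 gives three grounds for withdrawal: participant choice, non-compliance at one week, and loss of capacity.

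**The concern.** The hazard in 8.7 comes from taking digoxin and vitamin D together. A question about current use at entry controls it on the day of registration but not afterwards. The trial is run entirely remotely, so no clinic visit would bring a new prescription to light. If someone starts digoxin in month 6, the protocol relies on that person reporting a related event, and on the report or its follow-up naming the drug.

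A second gap follows. If the drug does come to light, the reviewers have no clear written instruction to stop capsules. Section 7.8 shows that the protocol does write on-treatment clinical rules: for loss of capacity it sets a trigger, doctor review, GP contact and withdrawal. It has nothing comparable for the one interaction it calls possibly severe.

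What is at stake is the safety of a small number of active-arm participants, who could stay on a combination that the protocol itself treats as a reason to bar entry.

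**Working it through.** **Step 1. Does any contact described after registration ask about digoxin?**

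| Contact | Section | Described content | Asks about digoxin? |
|---|---|---|---|
| Compliance call at one week | 7.8 | Whether study tablets are being taken | No |
| Assessments at 26, 52 and 104 weeks | 7.7 | Cognitive tests, daily living, EQ5D, behaviour scale | No |
| Medication diary | 8.11 | Online diary "which will ask participants to provide a quarterly tablet count" | No |
| Quarterly event prompt | 9.3 | Details of any events | No; events only |
| Call to absent participants | 9.3 | Health and wellbeing, after two missed timepoints | No |
| Capsule mail-out | 8.4, 8.5 | Labelling, dispatch, dispensing record | No check described |

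**Step 2. Could adverse event reporting reveal it?** Often, but indirectly. The illness that leads to a digoxin prescription would usually meet the 9.2 definition, because it is a medical event needing medical intervention. The record listed in 9.3 covers case description, duration, action taken, outcome, seriousness, causality and whether the event was anticipated. The drug might be named under description or action taken, but no item asks for medication. The 24-hour review applies to serious events; 9.3 gives no time limit for review of the rest. Digoxin started without a hospital admission would usually fall in that second group. The symptom warning in 8.7 concerns extreme overdose. It tells participants what to look for and says they are "provided with clear signposting to contact their GP for support if this occurs, in addition to reporting the event to the study administrator", but it is not directed at digoxin.

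**Step 3. Is there a stopping rule?** The sentence in 8.7 has no time limit, so it can be read as an entry rule or as a continuing one. None of the three grounds in 7.8 covers a new contraindicated medicine.

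**Step 4. How many participants?** The protocol gives no incidence of new digoxin use, so this is scale only.

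- Active arm: 584 / 2 = 292.
- Active person-years over the trial, with the 20% drop-out of section 10.1 assumed to be spread evenly over two years: 292 × (0.8 × 2 + 0.2 × 1) = 292 × 1.8 = 525.6.
- Expected new users = person-years × assumed annual incidence.

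| Exposure | Active person-years | 0.05% per year | 0.1% per year | 0.5% per year |
|---|---|---|---|---|
| Whole trial | 525.6 | 0.26 | 0.53 | 2.63 |
| 50% remaining at version 8.0 | 262.8 | 0.13 | 0.26 | 1.31 |
| 25% remaining | 131.4 | 0.07 | 0.13 | 0.66 |
| 10% remaining | 52.6 | 0.03 | 0.05 | 0.26 |

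The remaining shares are assumptions. Appendix A says only that, by version 8.0, power for the two-year outcome had already been achieved.

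**Step 5. Effect on the primary analysis.** Section 10.1 requires 234 participants per group, or 468 in total. One participant lost is 1 / 468 = 0.2% of that number.

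**The case against.** The strongest reply is that safeguards during dosing do exist. Quarterly prompts, reports at any time, review by at least two people, GP contact and the 24-hour rule for serious events would catch many cases, because the underlying illness usually qualifies as an adverse event whatever the participant thinks of the prescription. This stands. A reader might infer that new digoxin use would go undetected, or that detection depends on the participant regarding a prescription as an event. The documents do not support either reading. What remains is that the route is indirect and no question or field names the drug.

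Secondly, the exclusion in 8.7 is untimed and sits among the treatment sections, so a reviewer could take it as a standing direction. This also stands in part: the wording is unclear, and one cannot say that no rule of any kind exists. But no procedure carries the continuing reading into 7.8.

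Thirdly, the information sheet, welcome pack and full diary are not shown and may ask about new medicines. That would close the detection gap, though it would not settle the stopping rule.

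Fourthly, section 2.1 describes a non-medicinal supplement at a dose already on public sale, so light monitoring is a defensible choice. That argues for a small remedy; it does not explain why the one named severe interaction has no follow-through.

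**Conclusion.** The point holds as a low-severity safety improvement. On the text shown, digoxin is asked about once, no described contact during dosing asks again, and it is unclear whether the exclusion continues after entry. Following the protocol as written could therefore leave someone on a combination that it treats as contraindicated.

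The size is small: probably about one active-arm participant or fewer among those still on capsules at version 8.0. That rests on an assumed incidence of 0.05% to 0.5% per year and an assumed 10% to 50% of exposure remaining. The case rests on the severity that the protocol assigns to the interaction and on the low cost of the remedy, not on frequency.

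A reader might also infer a threat to the primary analysis, since 10.3 uses those with complete data at week 104 and 7.8 describes no assessments after withdrawal. The documents do not support that as a material effect. About one participant is involved, 10.3 plans multiple imputation as a secondary analysis, and the lack of assessments after withdrawal is common to every withdrawal and not specific to digoxin.

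**What to change.** 1. Add one yes/no item to the existing quarterly login prompt in 9.3, asking whether the participant has started taking digoxin. Flag a yes to the study clinician.
2. State in 8.7, with a matching entry in 7.8, that the digoxin exclusion continues during dosing. Capsules stop in either arm without routine unblinding, and outcome assessments continue to week 104. This makes it a treatment stop and not a withdrawal from the trial. Emergency unblinding under 7.5 stays available.

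If the information sheet or the diary already asks about new medicines, item 1 is unnecessary and only item 2 is needed.

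The cost is a protocol amendment, one item and one alert on a form that participants already open, and a few extra clinician reviews. Some placebo participants may occasionally stop capsules unnecessarily, which is the price of keeping the blind.

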## 7.2 Consent

Consent will be given by participants following the approved online, electronic processes in place within the PROTECT study. This process is already ethically approved and occurs as follows:

1. Participants first access the Participant Information Sheet via their PROTECT study homepage. The PIS will be presented in online and printable format, and participants are required to tick a box to confirm they have read and understood the document.
2. Participants will then be presented with a new website page with each consent item in the approved Informed Consent Form. They will have to tick each item individually before they can proceed.
3. Once complete, participants then tick a further tick-box on the same consent page to confirm they consent to take part in the study.
4. Finally, a separate confirmation page appears for participants to confirm that they are consenting on purpose. This process ensures consent cannot be given in error.

5. Consents are time- and date-stamped electronically and stored on the PROTECT study database, linked to study ID and pseudo-anonymised to allow for linkage to personal details in the event this information is required for future contact.

### 7.3 The randomisation scheme

Randomisation of participants will be achieved through a purpose-built algorithm embedded in REDCap Cloud. This functionality exists within the REDCap Cloud architecture and will be tailored to account for the specific randomisation and stratification requirements of the VitaMIND study. This will occur after a participant has consented to take part in the trial. The randomisation algorithm will allocate participants randomly, but will stratify them by:

- Age (age brackets of five years)
- Gender
- Vitamin D deficiency severity (mild-moderate (< 50 nmol/L) or severe (< 25 nmol/L) Vitamin D level)

### 7.4 Blinding

Treatment allocation of participants will be recorded electronically in REDCap Cloud which is hosted by the University of Exeter's Clinical Trials Unit. This will ensure that both participants and research team will be blind to allocation, thus removing any bias. Administrative staff on the overall PROTECT study team that have direct participant contact will not be involved in any data analysis in order to avoid any unconscious bias as a result of their contact.

